Of the SSEDs listed in Table 1, none provided a comprehensive, tabular summary of SAEs that corresponds with the composite list used for the statistical analysis of the primary safety endpoint of the AcQForce Flutter clinical study. The TOCCATTA trial²¹ was the first multicenter, randomized, controlled trial that used direct contact force in human subjects. The overall event rate for right sided ablations was 2.3%. A comparison of reported events within the SSEDs and the TOCCATTA trial to the pre-defined composite safety definitions suggests an approximate SAE mean event rate of 3.0%, and a weighted mean of 2.9% (Table 2). Note that rates reported in individual studies varied between 2.1% and 5.3%. To account for any differences between the AcQForce Flutter study's primary safety endpoint compared to the previous studies used in the meta-analysis, a derived safety event rate of 3% is expected. Based on this, a performance goal is proposed based on an expected rate of 98.5% and a 5.5% statistical margin. This will define the safety population sample size to support a primary safety endpoint with at least 90% power for the planned sample size.

		Acutus Pre-defined SAE								
Device Trade Name (PMA Number)	N	Death	Cardiac perforation / Pericardial Tamponade	Cerebral Infarct or Systemic Embolism	Myocardial Infarct	Major Access Site Complication	Major Bleeding requiring transfusion	Complete Heart Block	Other Device related SAEs / SADEs	Estimated Safety Event Rate
NaviStar [™] DS 8 mm Deflectable Diagnostic Ablation Catheter Celsius [™] DS 8 mm Deflectable Diagnostic Ablation Catheter Stockert 70 RF Generator (model 87001 with software version 001/033) Catheter Interface Cables (models D- 1195 and D-1170) (P010068)	182	Not Specified	Not Specified	Not Specified	Not Specified	1 (0.5%)	Not Specified	1 (0.5%)	2 (1.1%)	2.2%
IBI Therapyr [™] Dual 8 [™] Ablation Catheter IBI-1500T6 (USA) Cardiac Ablation Generator (P040042)	150	Not Specified	Not Specified	Not Specified	1 (0.6%)	Not Specified	Not Specified	Not Specified	7 (4.7)	5.3%
Therapy Cool Path Duo™ Ablation Catheter Safire BLU Duo™ Ablation Catheter 1500T9-CP Vi.6 Cardiac Ablation Generator (P110016)	188	1 (0.5%)	Not Specified	Not Specified	Not Specified	Not Specified	Not Specified	Not Specified	3 (1.6%)	2.1%
Therapy [™] Cool Flex [™] Ablation Catheter (P110016/ S008)	179	1 (0.6%)	Not Specified	1 (0.6%)	Not Specified	Not Specified	Not Specified	Not Specified	2 (1.1%)	2.2%

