8 STATISTICAL METHODS

8.1 Assumptions for Statistical Analysis

The following assumptions were used in the calculation of sample size:

Endpoint	Literature Based Control	Statistical Margin	Performance Goal	Acutus Estimate	(90% Power α 0.050)
Primary Safety	97.0%	5.5%	93.0%	98.5%	110
Primary Efficacy	93.7%	10%	83.7%	93.7%	85

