8.2 Statistical Methods for Safety Evaluation

The primary safety endpoint, the proportion of mITT and select ITT subjects who are free from device/procedure related SAE that occur through 7-days post ablation procedure, will be analyzed using a binomial proportion test. Subjects who do not have evidence of a SAE/SADE from the composite list of safety events will be considered a success.

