8.2.1 Primary Safety Endpoint Hypothesis

The null and alternate hypotheses for primary safety endpoint are as follows:

Ho: The proportion subjects in the mITT and select ITT subjects (ρ) who are free from device/procedure related SAE through 7-days post ablation procedure is less than or equal to 93.0%.

Ho:
$$\rho \le 93.0\%$$

Ha: The proportion subjects in the mITT and select ITT subjects (ρ) who are free from device/procedure related SAE through 7-days post ablation procedure is greater than 93.0%.

Ha:
$$\rho > 93.0\%$$

The null hypothesis will be rejected if the one-sided 95% Clopper-Pearson Exact lower confidence bound is greater than 93.0%.

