8.8 Study Sample Size Rationale

The sample size requirement for this protocol was determined using the Statistical Analysis System (SAS) Software (Cary, NC) Proc Power one sample proportion using a normal-approximate z test, with at least 90% power and a one-sided 5% significance level.

For the primary safety endpoint, assuming an estimated primary safety rate of 97% and a null hypothesis proportion of 93%, a minimum sample size of 110 subjects is required.

For the primary efficacy endpoint, assuming an estimated primary efficacy rate of 93.7% and a null hypothesis proportion of 83.7%, a minimum sample size of 85 subjects is required.

Therefore, the minimum required sample size for this study will be 110 subjects. A maximum of 120 mITT subjects will be enrolled.

8.9 Statistical Methods for Baseline, Screening, Procedural Experience and Hospital Discharge Data

Demographics, baseline data, including but not limited to relevant descriptors from the medical history, co-morbidities and medications, will be summarized.

Procedural data collection will also be analyzed and summarized.

Continuous variables are summarized as means, standard deviations, medians, and ranges. Categorical variables are summarized as frequencies and percentages. By-Subject listings of baseline and procedural data will be provided.

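### Section 8.8 sizes the safety endpoint at 110 from a 97% rate, but its own z test then needs 255; 110 follows only from a 98.5% rate that the protocol never derives

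*Combined protocol and SAP*

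**What the plan says.** Protocol 8.8 sizes both primary endpoints with a one-sample proportion procedure, "using a normal-approximate z test, with at least 90% power and a one-sided 5% significance level". For safety it states that, "assuming an estimated primary safety rate of 97% and a null hypothesis proportion of 93%, a minimum sample size of 110 subjects is required". For efficacy it takes 93.7% against 83.7% and obtains 85. The larger figure, 110, becomes the minimum for the study, and "A maximum of 120 mITT subjects will be enrolled".

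The assumptions tables in 3.2 and 8.1 carry the same 110 but separate two safety rates: 97% is the literature-based control and 98.5% is the "Acutus Estimate". Both tables show a 5.5% margin and a 93% performance goal.

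Section 3.2 gives the reasoning behind them. After averaging the Table 2 studies it concludes that "a derived safety event rate of 3% is expected". The next sentence says that "a performance goal is proposed based on an expected rate of 98.5% and a 5.5% statistical margin".

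The analysis is exact. Section 8.2.1, repeated in SAP 5.6.1.1, says: "The null hypothesis will be rejected if the one-sided 95% Clopper-Pearson Exact lower confidence bound is greater than 93.0" per cent. The endpoint is "the proportion of mITT and select ITT subjects who are free from device/procedure related SAE". Section 6.4.1 promises at least 90% power for each primary endpoint, and 8.4 requires both null hypotheses to be rejected.

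**The concern.** Section 8.8 is where a reader looks for the assumption behind the sample size. It says the trial has at least 90% power if the device merely matches the 97% literature rate. A 4-point difference near 97% should need far more than 110 subjects, so either the rate or the sample size is wrong.

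This endpoint matters most for the sizing: 3.2 says safety drives the sample size, and the study cannot succeed without meeting the safety goal. If 97% is close to the truth, the risk of missing that goal is several times the 10% that the plan implies. If 98.5% is the real assumption, the whole power statement rests on a rate for which the protocol gives no basis.

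**Working it through.** **Inputs.** One-sided alpha 0.05 (z = 1.645), power 90% (z = 1.282), and the normal-approximation z test, from 8.8. Safety null 93%; candidate rates 97% (8.8) and 98.5% (tables in 3.2 and 8.1). Efficacy 93.7% against 83.7% (8.8). Decision rule from 8.2.1.

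**Formula.** n = [(1.645·√(p0(1−p0)) + 1.282·√(p1(1−p1))) / (p1−p0)]²

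**Step 1: reproduce the plan's efficacy figure.** p0 = 0.837, p1 = 0.937: (0.6076 + 0.3114)/0.10 = 9.189, squared 84.4, so 85. This matches the plan and identifies the formula used.

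**Step 2: safety with the rate printed in 8.8.** p0 = 0.93, p1 = 0.97: (0.4197 + 0.2186)/0.04 = 15.957, squared 254.6, so **255**.

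**Step 3: safety with the tables' 98.5%.** p0 = 0.93, p1 = 0.985: (0.4197 + 0.1558)/0.055 = 10.463, squared 109.5, so **110**.

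**Step 4: could another version of the test give 110 from 97%?** At 90% power, using the alternative variance gives 156, continuity corrections give 180 to 280, and two-sided versions give 192 or more. The only near match is the alternative-variance form at 80% power, which gives 113. That contradicts the stated 90% and would give 37 for efficacy, not 85.

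**Step 5: power under the actual decision rule.** The rule allows at most 3 failures for every N from 109 to 128. Lower bounds are 93.10% for 107/110, 91.87% for 106/110, 93.67% for 117/120 and 92.53% for 116/120. Exact power is P(X ≤ 3), where X is binomial with the event rate shown:

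| N | True rate 97% (3% events) | True rate 98.5% (1.5% events) |
|---|---|---|
| 110 | 57.9% | 91.6% |
| 116 | 53.9% | 90.2% |
| 117 | 53.3% | 89.99% |
| 120 | 51.3% | 89.3% |

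The z test gives 50.0% at 110 for 97%. For 98.5% it gives 90.2% at 110 and 93.4% at 120, so it does not show the fall in exact power as N rises while the failure limit stays at 3. For 97%, the smallest N with 90% exact power is 257.

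**Step 6: the source of 98.5%.** The Table 2 counts give event rates of 4/182 = 2.2%, 8/150 = 5.3%, 4/188 = 2.1%, 4/179 = 2.2%, 3/109 = 2.8% and 5/152 = 3.3%. Pooled, 28/960 = 2.9%. An event rate of 1.5% is below all six. The goal follows from 98.5% (98.5 − 5.5 = 93.0) and not from the control (97 − 5.5 = 91.5). The 93% goal is 4.0 points below the control.

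**The case against.** The strongest reply is that this is a transcription slip. The assumptions table in 8.1 lists 98.5%, 93.0% and 110, the table in 3.2 repeats them, and at 98.5% the sample size is right. On that reading a miss rate computed at 97% does not describe the design, and a wording correction does not deserve a high rating.

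Much of this is fair. The 97% in 8.8 is probably the control value carried into the text, and 110 is correct for 98.5%. But 8.8 still makes a false power statement, and changing one number does not repair 3.2, which moves from an expected 3% event rate to a 1.5% rate without explanation. Once 98.5% is named as the assumption, power at 97% is the relevant sensitivity figure, because 97% is the only rate the protocol derives.

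Other points stand in part:

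- Section 3.2 says in words that the 5.5% margin goes with 98.5%, so labelling the tables is only a clarification.
- The shortfall at 120 under 98.5% is 0.7 points and comes from the discreteness of the exact rule.
- Section 3.2 concedes that its SSED sources have no event summary matching the composite, so Table 2 leaves 98.5% unsupported but does not disprove it.
- The 110 and 120 are mITT counts. The safety denominator adds ITT failure subjects who had the catheter inserted, and SAP 5.3 drops missing values, so N can fall outside that range. At 98.5%, exact power is 77.9% at N = 108 (2 failures allowed), 87.3% at 128 and 95.4% at 129 (4 allowed).

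**Conclusion.** The concern holds. The inputs printed in 8.8 require 255 subjects, not 110. The 110 comes from 98.5%, which the protocol states but does not derive. At the 97% rate that 8.8 names, a device would miss the safety goal about 42% of the time with 110 subjects and 49% with 120, against the 10% implied. Even at 98.5%, exact power reaches 90% only for N from 110 to 116 within the 110–120 range.

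These figures assume independent subjects with a common event rate and complete safety data at each N. The performance goal, the decision rule and the type I error are not affected. The fault is a sample size and power statement that its own inputs do not deliver, for the endpoint that sizes the trial, so it must be corrected.

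**What to change.** - **8.8:** replace 97% with 98.5%, the rate that produces 110.
- **3.2:** reconcile the expected 3% event rate with 98.5% and give the basis for 98.5%.
- **6.4.1 and 8.8:** state that the safety power is conditional on a true rate of 98.5%. Give exact power at 98.5% (91.6% at 110, 89.3% at 120) and at 97% (57.9% at 110, 51.3% at 120). Say that N here is the number of subjects in the safety analysis, which can differ from the mITT count.
- **Tables in 3.2 and 8.1:** keep 5.5%, label it as measured from the 98.5% estimate, and note that the goal is 4.0 points below the 97% control.
- **While editing 3.2:** reconcile its maximum of 110 with the 120 in the synopsis, 6.4.1 and 8.8.

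The cost is wording and figures in four sections. It needs no extra patients and no change to the 93.0% goal, the test, or the 110 minimum and 120 maximum in 8.8. The stated power becomes less favourable.

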8.10 Other Statistical Considerations

Confidence intervals and statistical tests are performed at a two-sided 5% significance level unless specified otherwise. All p-values are rounded to four decimal places. Analyses of the study may be utilized for publication or medical conference presentation purposes if the integrity and objectives of the study are not compromised.

9 ADVERSE EVENTS

For the purpose of this CIP/protocol, an adverse event is any untoward medical occurrence, unintended disease or injury, or any untoward clinical signs in subjects whether or not related to the AcQBlate Force Sensing System, and includes events related to the procedures involved in the CIP/protocol.

Any medical conditions, problems, signs, symptoms, or findings that occurs in a subject once they are considered a component of the "Intention to Treat" is considered an adverse event (AE). Any medical conditions, problems, signs, symptoms, and findings occurring prior to enrollment are to be reported as pre-existing conditions on the Medical History eCRF.

All AEs will be documented with the event term and description, start date, duration, severity, seriousness, relatedness to either the device or the procedure, action taken, and outcome, will be recorded on the Adverse Event eCRF. The Investigator has the responsibility of classifying any event as related to a component of the AcQBlate Force Sensing System, or the ablation procedure.

9.1 Serious Adverse Events/Serious Adverse Device Effect

A Serious Adverse Event/ Serious Adverse Device Effect is any event that:¹

- led to death
- led to serious deterioration in the health of the subject, that either resulted in:
 - a life-threatening illness or injury, or
 - a permanent impairment of a body structure or a body function including chronic diseases, or
 - in-patient or prolonged hospitalization, or
 - medical or surgical intervention to prevent life-threatening illness or injury or permanent impairment to a body structure or a body function
- led to fetal distress, fetal death, or a congenital anomaly or birth defect

Reports relating to the subject's subsequent medical course following an SAE must be submitted to the Sponsor until the event has subsided or, in the event of permanent

¹ EN ISO 14155:2011 section 3.37

impairment, until the event has stabilized, and the overall clinical outcome has been ascertained.

A planned, in-patient hospitalization, without a serious deterioration in health, is not considered to be an SAE.

Recurrence of atrial flutter is not considered an adverse event as there is a known recurrence rate associated with atrial flutter ablation. Scheduled hospitalizations to treat these arrhythmias will not be considered serious in nature. However, if a subject is hospitalized for a clinical condition resulting from the arrhythmia, an adverse event should be reported.

9.2 Adverse Device Effects (ADEs)

Adverse Device Effects (ADEs) are a subset of AEs. The ADEs are only those AEs caused by, or related to the device, including any AE resulting from insufficiencies or inadequacies in the instructions for use, the system components, or any product malfunction, including any event that is a result of a user error or intentional misuse.

With any procedure or treatment, there are known possible risks and complications. A list of known or anticipated ADEs is found in the CIP/protocol, IFU, and Operator's Manual (OM).

9.3 Unanticipated Adverse Device Effects (UADEs)

An Unanticipated Adverse Device Effect is any event that occurs as a result of the device use that was not identified as a known or an anticipated risk for the AcQBlate Force Sensing System, as found in the CIP/protocol, IFU, and OM for the device.

When an Investigator suspects an event meets the definition for a UADE, the event term and description, start date, duration, severity, seriousness, relatedness to either the device or the procedure, action taken, and outcome, will be recorded on the Adverse Event eCRF. Additionally, reports must be provided to the reviewing Institutional Review Board/Ethics Committee/Competent Authority (IRB/EC/CA) per national and local requirements.

The Sponsor/manufacturer must then conduct an evaluation of the suspected UADE and report the results of the findings to all reviewing IRBs/ECs/CA and participating Investigators within five (5) business days after first receiving notice of the effect.

9.4 Adverse Event Reporting

The Investigator is responsible for reporting all procedure and device related AEs that occur during the follow-up period. Initial reporting will be with the Adverse Event eCRF; however, additional information may be required by the Sponsor or any regulatory authority. The Investigator must report any SAEs, SADEs, UADEs, or Device Deficiency (DD) to the Sponsor as soon as possible after becoming aware of the event, but no later than ten (10) business days after receiving knowledge of the event occurrence. All SAEs, SADEs, and UADEs will be documented on the Adverse Event eCRF along with an explanation of any medical treatment administered. Documentation should include the time of onset, complete description of the event, severity, duration, actions taken, and outcome.

9.5 Event Relationship to the Device

The Investigator should provide information regarding the relationship of the event to the procedure and/or the AcQBlate Force Sensing System. The device relationships and severity definitions are defined in Tables 10 and 11 below:

Table IV. Auve	ise Event Relationship Definitions
Not Related	The cause of the AE is known and is not related to any aspect of the
	AcQBlate Force System during the ablation procedure.
Possibly	There is a reasonable possibility that the event may be related to the
Related	ablation procedure. The AE has a timely relationship to the study
	procedure(s); however, it follows no known pattern of response and
	an alternative cause seems more likely or there is significant uncertainty.
Probably	It is probable that the event is related to the ablation procedure. The AE
Related	has a timely relationship to the study procedure(s) and follows a known pattern of response , but a potential alternative cause may be present.
Definitely	The event is definitely related to the ablation procedure. A related event
Related	has a strong temporal relationship and an alternative cause is unlikely.

 Table 10. Adverse Event Relationship Definitions

Table 11. Adverse Event Severity Definitions

Mild	Event results in mild or transient discomfort, not requiring intervention or treatment; does not limit or interfere with daily activities (e.g., insomnia, mild headache).
Moderate	Event is sufficiently discomforting so as to limit or interfere with daily activities; may require interventional treatment (e.g., fever requiring antipyretic medication).
Severe	Event results in significant symptoms that prevents normal daily activities; may require hospitalization or invasive intervention (e.g., anemia resulting in blood transfusion).

9.6 Death Notice

When a site becomes aware of a subject's death, it will be reported to the Sponsor. Notification should be made to the reviewing IRB/EC/CA/local requirements within two (2) days of notification. The FDA will be notified within 10 days.

The materials to be submitted to the Sponsor for a death include the following:

- Death narrative including a short description by the treating physician of record at the time of death regarding the circumstances of death.
- An assessment by the Investigator as to whether the death is related to study interventions.
- A copy of the subject's death certificate if available.
- When applicable, a copy of an autopsy report.

For reported deaths, the Investigator or designee should supply the Sponsor and the presiding IRB/EC/CA with any additional requested information, if available (i.e., hospital records).

9.7 Device Complaint and Malfunction

Each clinical procedure will be attended by Acutus Medical personnel responsible for the proper use of the technology. If a malfunction occurs, the Sponsor representative will report the findings to the Clinical and Product Complaints departments. Evaluations of all complaints will follow Acutus Medical Quality Assurance Procedures (QAPs) for complaint handling.

9.8 Adverse Event Analysis

All procedure and device related AEs will be independently adjudicated. Analysis of data will follow the Safety Management Plan and the Statistical Analysis Plan. Reporting to the convening IRB/EC will follow regulatory requirements.

9.9 Clinical Events Adjudication

Acutus Medical, Inc. (or designee) will coordinate meetings with the clinical events adjudication reviewer in accordance with Acutus Medical, Inc. QAP and the Safety Management Plan for AcQForce Flutter. The selection of a qualified individual will allow for the evaluation of individual safety events for adjudication and comment on the overall conduct of the clinical trial. The qualified individual will assume the following roles:

- To review and independently adjudicate safety data by providing a standard, methodical, independent, and unbiased assessment of safety events and relationship to the clinical trial.
- To adjudicate individual adverse events within the clinical trial to determine if those events are related to the clinical trial or the investigational device.
- To periodically review and evaluate the accumulated safety data to assure the safety of subjects is protected while the scientific goals of the clinical trial are being met.

• To monitor safety data trends, reviewing issues critical to the conduct of the clinical trial as data is generated.

10 RISK: BENEFIT ANALYSIS

10.1 Risks of Clinical Study Procedures

This clinical study has been designed to involve as little pain, discomfort, fear, and any other foreseeable risk as possible for the enrolled subjects. Even when the AcQBlate Force Sensing System is used correctly, complications during and after the ablation treatment may occur.

The following AEs are associated with electrophysiology right atrial ablation procedures:

- Air embolism
- Acute Respiratory Distress Syndrome (ARDS)
- Allergic reaction/anaphylaxis
- Anemia
- Anesthesia reaction
- Arrhythmias
- AV fistula
- Cardiac tamponade/perforation
- Cardiac thromboembolism
- Chest pain/discomfort
- Complete heart block
- Congestive heart failure
- Coronary artery spasm
- Death
- Diaphragmatic paralysis
- Elevated Cardiac Enzymes
- Endocarditis
- Esophageal
 - abrasion/erosion/perforation
- Femoral nerve injury
- Fever
- Groin hematoma/ecchymosis
- Hemothorax
- Hypotension
- Hypothermia
- Infections/sepsis
- Major bleeding requiring surgery or transfusion

- Myocardial infarction
- Obstruction, perforation or damage to the vascular system
- Oral pharyngeal injury
- Pericardial effusion
- Pericarditis
- Phrenic nerve damage
- Pleural effusion
- Pneumonia
- Pneumothorax
- Pseudoaneurysm
- Pulmonary edema
- Pulmonary embolism
- Pulmonary hypertension
- Radiation injury
- Respiratory depression
- Retroperitoneal bleeding
- Skin burns
- Stroke
- ST segment elevation
- Systemic embolism
- Thromboembolism
- Tracheal injury
- Transient ischemic attack
- Valvular damage/insufficiency
- Vasovagal reactions
- Vagal nerve injury /gastroparesis

The following ADEs may be experienced if the IFU is not followed:

- Injury to user during defibrillation.
- Excessive force, if applied, may damage the AcQBlate FORCE catheter sensor at the distal section.
- The AcQBlate FORCE may be damaged through introducer sheath if the transseptal sheath lumen is less than 8.5F.

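### The UADE definition in 9.3 tests only whether a harm was identified, so an excess or unexpected severity of a harm listed in 10.1 does not start the timed notice to all sites

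*Combined protocol and SAP*

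**What the plan says.** Protocol 9.3 defines a UADE as "any event that occurs as a result of the device use that was not identified as a known or an anticipated risk", the reference being risks "as found in the CIP/protocol, IFU, and OM for the device". For a suspected UADE the sponsor must evaluate the effect and report its findings to all reviewing IRBs/ECs/CAs and all participating investigators within five business days of first notice.

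Protocol 9.2 places one such list in the protocol itself: "A list of known or anticipated ADEs is found in the CIP/protocol", alongside the IFU and the Operator's Manual.

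Protocol 10.1 holds two lists. The long one is introduced by "The following AEs are associated with electrophysiology right atrial ablation procedures" and has 52 entries, including Death, Stroke, Myocardial infarction and Cardiac tamponade/perforation. No entry has an expected rate. Explicit severity wording is confined to an entry such as "Major bleeding requiring surgery or transfusion". The short list is introduced by "The following ADEs may be experienced if the IFU is not followed" and has three entries: injury to the user, and two forms of damage to the catheter.

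**The concern.** The definition asks one question: was this harm already identified? A harm named in the reference documents stays anticipated however often it occurs and however severe it is. The long list names most of the serious harms one would want to watch with a new ablation catheter, so the rule does not reach an unexpected cluster of a known complication.

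At stake is the speed at which sites learn of such a cluster. Section 9.3 is the only rule that obliges the sponsor both to evaluate a harm and to tell every investigator and every IRB/EC/CA by a fixed deadline. If it does not start, other sites may go on treating subjects without timed notice. Section 10.2 says that new information altering the risk will be communicated, but gives no trigger and no time limit.

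**Working it through.** **1. The rule against the list.** The plan states no figure to reproduce here, so the main check is textual.

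- 9.3 has one criterion, prior identification. Severity and frequency are not mentioned.
- 10.1 gives names without expected rates.
- So an excess of a named harm leaves its status under 9.3 unchanged. More entries in the IFU or Operator's Manual would only add identified risks. Rates stated there would have no role, because 9.3 does not test rate.

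**2. What else would act on an excess of a listed harm.**

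| Section | Duty | Timed notice to all investigators? |
|---|---|---|
| 9.4 | Investigator reports SAEs, SADEs and UADEs to the sponsor within 10 business days | No |
| 9.6 | Death goes to the sponsor, to the reviewing IRB/EC/CA within 2 days and to FDA within 10 days | No |
| 9.9 | Independent reviewer periodically evaluates accumulated safety data and monitors trends | No; no threshold, deadline or duty to notify |
| 10.2 | Sponsor communicates information that alters the risk | No time limit or trigger |
| 13.2, 13.3 | IRB/EC and CA kept informed of SAEs and SADEs | No |
| 14.1 | Notice within five business days of deciding to suspend or terminate, with a report to all investigators | Only after that decision |

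Section 11.17.3 also sets a five-business-day notice to investigators, but only when regulatory approval is withdrawn. SAP 5.9 plans no interim analysis.

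**3. Illustration of size.** Inputs are the tamponade/perforation cells of Table 2. Two studies report the event, 1 of 109 and 2 of 152. The other four are marked as not specified.

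Pooled rate: (1 + 2)/(109 + 152) = 3/261 = 1.15%. Expected events in 20 subjects: 20 × 0.0115 = 0.23.

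P(at least 3 of 20) = 1 − Σ C(20,k) p^k (1−p)^(20−k), for k = 0, 1, 2:

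| Assumed rate p | Basis | P(at least 3 of 20) |
|---|---|---|
| 0.31% | 3/960, if the four silent studies had no events | 0.003% |
| 1.15% | 3/261 | 0.15% |
| 2% | assumption | 0.7% |
| 3.3% | upper limit of the exact 95% interval for 3/261 | 2.7% |

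Such a cluster would be surprising across this range. With 10.1 as the reference list, 9.3 would still class it as anticipated.

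**4. The only numeric limit on harm in the documents.** This is the final test of the composite endpoint (one-sided 95% Clopper-Pearson lower bound above 93.0%). With 3 failures the bound is 93.1% at n = 110 and 93.7% at n = 120, so the test passes. With 4 it is 91.9% and 92.5%, so it fails. The test comes at the end and covers the composite. It is neither a UADE trigger nor a limit on any single harm.

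**5. Can Table 2 supply trigger rates?** Reported rates, pooled over the studies that give a count:

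- death: 2/(188 + 179) = 0.54%
- myocardial infarction: 1/150 = 0.67%
- complete heart block: 1/182 = 0.55%
- bleeding requiring transfusion: no figure in any of the six studies

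One event is 1/110 = 0.91% or 1/120 = 0.83% of the trial. The first death, infarction or heart block would therefore always exceed its rate, so a trigger of this kind would not discriminate.

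**The case against.** **Other oversight exists.** A reader might infer that an excess of a listed harm would go unnoticed, or that a device-caused death would start no clock. The documents do not support that. The reporting and review duties set out above apply whether or not an event is listed, and 9.6 sets its own deadlines for deaths. This objection stands, and it confines the gap to the UADE rule and its timed notice to all sites.

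**The long list may not be the reference list.** It is headed as risks of right atrial ablation procedures, and 10.2 treats it as the risks of a standard ablation, whereas 9.3 asks about risks of the AcQBlate system. If only the short list counted, a reader might infer that every device-caused harm to a subject is unanticipated. That goes too far, because 9.2 and 9.3 also name the IFU and Operator's Manual. What stands is an ambiguity about which list governs. It does not rescue the rule: whichever list applies, severity and frequency are not part of the test.

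**Severity is not wholly absent.** This is correct. The major-bleeding entry carries a qualifier, and Table 6 sets severity thresholds for most composite events. Section 3.2 also gives an expected composite event rate of 3%. None of these is linked to 9.3 or 10.1.

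**Unseen documents.** The IFU, Operator's Manual, Safety Management Plan and risk analysis were not available, and any of them could hold rates or escalation triggers. This stands as a limit on the conclusion. The general commitment in 13.1 to follow the CFR does not settle the matter, because 9.3 states its own definition and refers to no other.

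**The tamponade example is constructed.** This is fair. It rests on three events in two studies, and two of those events come from a study that, according to 3.1, also treated paroxysmal atrial fibrillation. It shows scale only.

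**Conclusion.** The concern holds in a limited form. As 9.3 is written, a device-related excess or unexpected severity of a harm already identified in the reference documents does not start the five-business-day evaluation and notice to all IRBs/ECs/CAs and investigators. No other provision supplies a timed notice to all sites of such an excess short of suspension or termination.

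The gap concerns how fast and how widely an excess is reported. It does not show that harms go unreported, and it affects no endpoint, sample size or test. No rate can be attached to its practical effect. The 0.15% figure, with its range of 0.003% to 2.7%, only shows how unusual a cluster could be and still fall outside the rule.

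The conclusion assumes that 9.3 is applied as worded and that the documents not supplied do not add a severity or frequency test. The tamponade illustration further assumes that the event is identified in 10.1 or in one of the other two reference documents. The point is worth correcting because it is a safety rule and the change is small.

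**What to change.** 1. In 9.3, define a UADE as a device effect not previously identified in nature, severity or frequency.
2. In 9.9, have the independent reviewer's trend review judge whether a listed event is more frequent or more severe than anticipated, and send any such event through 9.3.
3. In 9.2 and 10.1, state which of the two lists, together with the IFU and Operator's Manual, is the list of anticipated device effects.
4. Cite Table 2 rates only as context, where a rate is reported. Do not use them as automatic triggers.

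The cost is protocol wording and a few more sponsor evaluations. Endpoints, sample size and clinical management stay as they are.
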